10.1.2 Analyses of Continuous Variables

Change from baseline in PSS will be analyzed by stratified van Elteren test. For other continuous variables, the model based mean and standard error will be presented. The Baseline and visit means will also be presented for each treatment group for subjects who

have both Baseline and post Baseline visit values. The treatment groups will be compared using ANCOVA with treatment group, Baseline value, and stratification factors in the model.

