7.3.3 Further endpoint analyses

Change from baseline in PSS at Week 16 will be analysed by the van Elteren test between the BI 655066 arm and placebo arm. The other further endpoints will be summarised descriptively, with number and proportion of responders for dichotomous endpoints and mean, median, SD and IQR presented for continuous variables.

Time to onset of *Endpoint*, the time to event will be calculated as:

- Time to first onset (with observed event) = [date of first onset] – [date of first active treatment] + 1
- If a patient never attains *Endpoint* (e.g., PASI75 or PASI90), then that patient's time to first onset will be censored at the last visit where the *Endpoint* was measured (e.g., PASI).

Time to Loss of *Endpoint* (from time of randomisation), defined using the following algorithm:

- a) Never attains *Endpoint* (Failure at time 0)
- b) After achieving *Endpoint*, patient will be a failure if they subsequently do not achieve *Endpoint* and either discontinue from the study or switch therapy

while still not achieving *Endpoint*. Time to failure will be calculated using date of first failure to achieve *Endpoint*.

- c) Patients randomised to placebo will have Week 16 (i.e. when they begin taking BI 655066) as Day 0 for determining Time to Loss of response.
- d) Patients who maintain *Endpoint* throughout the study will be censored at their last measurement

Time to Loss of *Endpoint* (from time of achieving *Endpoint* or from specific point in time) will be defined as above but only for those patients that have achieved *Endpoint*.

All Time to Event endpoints will be presented using Kaplan-Meier curves.

As sensitivity analysis, the primary and secondary endpoints will be analysed in the same way based on PP Population.

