10.1.5 Analysis of Psoriasis Symptoms Scale (PSS)

The 4-item PSS was designed to measure patient-reported psoriasis symptoms. Subjects are requested to rate the severity of each of their symptoms related to pain, redness, itching, and burning, in the last 24 hours from "0 = none" to "4 = very severe," with total scores, which is the sum of the four item responses, ranging from 0 to 16 with higher scores indicating worse symptoms. If one or more of the four items are missing then the total score for that day will be set to missing.

PSS will be completed on Day 1 and the Week 16 visit in Part A. Total Score from Day 1 will be used as the baseline value. Change from baseline in PSS will be analyzed by the van Elteren test between the risankizumab arms and placebo arm using the stratification factors of Concomitant PsA at baseline (Yes: Diagnosed or Suspected; versus: No) and body weight (≤ 90 kg versus > 90 kg). An example of the SAS code for this is as follows:

```
proc freq data = indata;  
  
tables strata * treatment * aval1 / cmh2 scores=modridit nopol;
```

where "strata" is numbered 1 – 4 based on the row order, "treatment" is dichotomous (Arm A or Arm B), and "aval1" is the PSS change from baseline at Week 16. In the output from this code, the p-value is the "Prob" for statistic 2 – "Row Mean Scores Differ."

PSS will be completed by the subject during clinic visits at Week 28, Week 40 and Week 52 in Part B. The PSS change from baseline will be summarized for these visits for each treatment arm.

In addition to the PSS total score, the four individual components, pain, redness, itching, and burning, will be analyzed using the same methodology.

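### Week 16 PSS change is tested by an unadjusted van Elteren test with no between-arm estimate or CI specified; adding the SAP's own baseline-adjusted ANCOVA is a cheap, optional improvement

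*SAP*

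**What the plan says.** Protocol 7.3.3 names the test: "Change from baseline in PSS at Week 16 will be analysed by the van Elteren test between the BI 655066 arm and placebo arm". For the rest of that endpoint class it adds that "The other further endpoints will be summarised descriptively". PSS change is therefore the only further endpoint for which the protocol names a between-arm test.

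SAP 10.1.2 repeats the choice: "Change from baseline in PSS will be analyzed by stratified van Elteren test". For the other continuous variables it calls for model-based means and standard errors, and states: "The treatment groups will be compared using ANCOVA with treatment group, Baseline value, and stratification factors in the model".

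SAP 10.1.5 describes the total score as "ranging from 0 to 16 with higher scores indicating worse symptoms". It has PSS completed on Day 1 and at Week 16 in Part A, and gives example code: "tables strata * treatment * aval1 / cmh2 scores=modridit nopol". The only output it takes from that code is the row-mean-score p-value. It then says that "the four individual components, pain, redness, itching, and burning, will be analyzed using the same methodology". The summaries of PSS change by arm that it mentions are for Weeks 28, 40 and 52.

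**The concern.** Two things are missing from the Week 16 analysis of PSS change.

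The first is the baseline. The room a patient has to improve on a 0 to 16 score depends on where that patient starts. In an arm that nearly clears, the change is largely minus the Day 1 value. Ranking the raw change within strata leaves that variation in the comparison, although Day 1 PSS is collected. Boundedness does not explain the choice. DLQI is also a bounded patient-reported score (0 to 30, Protocol 10.4.2), and its change from baseline falls under the ANCOVA rule.

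The second is an effect size. A p-value does not tell a reader how many points symptoms improved relative to placebo, or with what uncertainty. This applies to the total and to the pain, redness, itching and burning items.

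At stake are the precision and readability of the main patient-symptom comparison. The primary result is not affected.

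**Working it through.** **The plan's own figure.** The documents state no SD, correlation, effect size or power for PSS. Their only sample-size figure is for PASI 90 (Protocol 7.7: 65% v 5%, two-sided 5%, 95% power). It reproduces: the two-proportion formula gives 14 per arm without continuity correction and 17 with it, and 17 is the protocol's number. It says nothing about PSS, so everything below rests on assumed inputs.

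**Variance.** Let baseline and Week 16 PSS have equal SD σ and correlation ρ.
- Change score, per-patient variance: 2σ²(1 − ρ)
- ANCOVA, residual variance: σ²(1 − ρ²)
- Ratio: (1 − ρ²) / [2(1 − ρ)] = (1 + ρ)/2

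The ratio is 0.60 at ρ = 0.2, 0.70 at 0.4, 0.80 at 0.6 and 0.90 at 0.8.

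As an illustration, take σ = 3.5 (assumed), ρ = 0.4 and 56 per arm (Protocol 7.7), so √(2/56) = 0.189.
- Change score: SD 3.5 × √1.2 = 3.83, SE 0.72, 95% half-width 1.42 points
- ANCOVA: SD 3.5 × √0.84 = 3.21, SE 0.61, 95% half-width 1.19 points

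**Power by simulation.** Scores were rounded and clipped to 0–16, with mean 8 and SD 3.5. There were 56 v 56 patients and four strata (each factor at an assumed 15% prevalence), with 2,000 trials per setting. Entries are van Elteren on change v ANCOVA with baseline and strata.

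| Effect | ρ = 0.2 | ρ = 0.4 | ρ = 0.6 | ρ = 0.8 |
|---|---|---|---|---|
| 0.5 SD | 51% v 74% | 61% v 81% | 78% v 88% | 97% v 99% |
| 1.0 SD | 98% v 100% | >99% v 100% | 100% v 100% | 100% v 100% |
| 1.5 SD | 100% v 100% | 100% v 100% | 100% v 100% | 100% v 100% |

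With no effect, rejection rates were 4.4% to 5.8% for both methods.

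A stratified rank ANCOVA falls between the two. At a 1.5-point difference and ρ from 0.2 to 0.6, van Elteren had 39–67% power, rank ANCOVA 58–74% and ANCOVA 61–78%.

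**Single items (0–4, assumed inputs).** With baseline mean 1.2 and Week 16 means of 1.0 v 0.4, power at ρ = 0.2, 0.4 and 0.6 was 63%, 72% and 87% for van Elteren, against 94%, 95% and 99% for ANCOVA. With baseline mean 1.9, SD 1.1 and a 1-point effect, van Elteren already had 93–99.5%.

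**Where the direction reverses.** Scores were again clipped to 0–16, but with heavy-tailed errors and a 0.7-point shift. van Elteren had 53% v 49% for ANCOVA (baseline slope 0.8, t errors with 3 df) and 54% v 36% (slope 1.0, 2 df). At slope 0.5, ANCOVA stayed ahead for 1.5, 2 and 3 df.

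**The case against.** The strongest reply is that nothing here is wrong. The protocol synopsis, Protocol 7.3.3, SAP 10.1.2 and SAP 10.1.5 all name the same test. It is stratified by the randomisation factors and keeps its error rate, and a rank test is a defensible choice for a discrete, bounded score. Chance imbalance in Day 1 PSS is already covered by that error rate, and SAP 7.1 compares baseline PSS across arms. PSS change is a further endpoint, and the testing order in SAP 10.4 covers PASI 90 only. The sponsor also plans on a large effect. On a latent normal scale, 65% v 5% is a separation of 0.385 + 1.645 ≈ 2.0 SD. PSS is a different measure, but if its effect is anywhere near that size, both tests are certain to reject.

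All of that stands, and it rules out several stronger readings that a reader might infer:
- **The test is invalid or contradicts the protocol.** It is valid, and the documents agree.
- **Precision is certainly lost.** This depends on a correlation and distribution that the documents do not give, and it can reverse. The reversal needs heavy tails and a baseline slope near 1, which is unlikely in an arm that largely clears, but it cannot be excluded.
- **PSS has no effect estimate.** PSS = 0 (SAP 10.3.1) is binary and gets the risk difference with 95% CI of SAP 10.1.1. The list of tables in SAP 17.0 is not in the supplied text, so a descriptive Week 16 table cannot be ruled out either.
- **van Elteren should become merely supportive.** That would create a protocol–SAP difference over the lead method where none exists now.

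The objection does not answer the missing Week 16 difference and interval. That gap needs no simulation assumption.

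**Conclusion.** The concern holds in a limited form. In the supplied text, Week 16 PSS change (total and four items) gets a p-value from a test that takes no account of Day 1 PSS, and no between-arm estimate or CI. Other continuous efficacy variables, including the similarly bounded DLQI, get baseline-adjusted ANCOVA.

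Baseline adjustment would likely help. Under equal SDs and ρ from 0.2 to 0.6, variance falls to about 60–80% of the change-score variance, so intervals are roughly 11% to 23% narrower (1 − √0.80 and 1 − √0.60). The power gain is up to about 23 points at 0.5 SD and 0 to 2 points at 1 SD or more. It is most likely to matter for single items with modest effects. No confirmatory conclusion changes, so this is an optional, cheap improvement.

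**What to change.** In SAP 10.1.2 and 10.1.5, keep the stratified van Elteren test as the protocol-named test of Week 16 PSS change. Beside it, for the total and each of the four items, add the ANCOVA already specified in SAP 10.1.2 (treatment, Day 1 PSS value, stratification factors). Report the adjusted difference from placebo with its 95% CI for each risankizumab arm. If an adjusted test based on ranks is preferred, use a stratified rank ANCOVA, and still report a difference with an interval.

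No data collection changes and no patient is lost, because a change score already requires Day 1 PSS. One caution applies: in an arm that nearly clears, the slope of Week 16 on Day 1 PSS may be flatter than on placebo. The common-slope difference should then be read as an average effect.

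The cost is one extra output per PSS variable and an entry in SAP 14.1. The addition should be specified before the statisticians are unblinded for the Week 28 analysis; if made later, it should be labelled post hoc.

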7.7 DETERMINATION OF SAMPLE SIZE

The study is powered to show a benefit of BI 655066 over placebo in terms of PASI 90 response at Week 16. Based on the outcome from the trial 1311.2, the PASI 90 response rate at Week 16 is assumed to be at least 65% in the BI 655066 arm. There is only minimal data available on placebo response in the BI 655066 program but the phase 3 results from ustekinumab and secukinumab indicate a response rate for PASI 90 of approximately 5% in the placebo arm. With 2-sided significance level 5%, based on these assumptions (65% vs 5% PASI 90 response rates), 17 patients in the BI 655066 arm and 17 in the placebo arm will provide 95% power for each comparison and an overall power of at least 90%.

For the Japanese submission, the safety data of at least 100 Japanese patients exposed to BI 655066 at the registered dose(s) for 1 year or more is necessary for long team safety assessment as a result of the PMDA consultation meeting in 2015. This study will enrol a total of 168 patients, with 56 patients in each of the two BI 655066 arms and 56 patients in the placebo arm. It is expected that at least 68 patients exposed to BI 655066 75 mg and 68

Proprietary confidential information © 2017 Boehringer Ingelheim International GmbH or one or more of its affiliated companies

patients exposed to BI 655066 150 mg will reach at least 1 year exposure to BI 655066 in this clinical trial or in the following extension study. Other global phase III trials where Japanese patients are to be enrolled will make up for the remaining safety data requirements.

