10.0 Efficacy Analysis

10.1 General Considerations

When the last patient completes the Week 28 visit, the Primary Analysis will be performed including all efficacy endpoints pertaining to Part A. This is the only and final analysis for these endpoints, hence no alpha adjustment is required. For this primary analysis, all endpoints will be analysed up to Week 28, with the following exception:

- Categorical endpoints related to PASI and sPGA, using the LOCF method, will be analysed up to the last visit that at least one subject has observed PASI and sPGA measurements, respectively.

The treatment effect will be evaluated based on a two-sided significance level of 0.05 (when rounded to three decimal places).

The ITT population will be used for the analyses of efficacy endpoints. The following treatment periods will be analyzed:

- Part A (up to Week 16)
- Part B (Week 16 and after)

Time-to-event analysis will be performed across the entire study for subjects who are randomized to risankizumab or placebo arms in addition to the analyses in Part A.

Primary variable will also be analyzed for the per-protocol populations using primary approach to handle missing data as described in Section [10.1.4](#).

Subjects' actual Concomitant PsA at baseline (Yes: Diagnosed or Suspected; versus: No) and body weight (≤ 90 kg versus > 90 kg) will be used as the strata in the stratified analyses.

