10.3.1 Further Efficacy Analysis

Further exploratory endpoints below will be analyzed among the ITT Population at all visits collected:

- Achievement of PASI 50/75/90/100
- Achievement of sPGA of clear and sPGA of clear or almost clear
- Time until the first achievement of PASI 50, PASI 75, PASI 90, PASI 100, sPGA of clear and sPGA of clear or almost clear
- Time until loss of PASI 75, PASI 90, PASI 100, sPGA of clear and sPGA of clear or almost clear response
- Change from baseline in PASI score
- Percent change from baseline in PASI
- Achievement of absolute PASI of < 3
- Change from baseline in psoriasis symptoms evaluated using the total score on the Psoriasis Symptoms Scale (PSS)
- Achievement of a Dermatology Life Quality Index (DLQI) score of 0 or 1
- Achievement of total score on the PSS of 0
- Change from baseline in DLQI
- Change from baseline in HAQ-DI, among subjects with confirmed diagnosis of PsA using CASPAR criteria and with baseline total TJC and SJC counts ≥ 3 at selected study sites
- Change from baseline in Pain VAS, among subjects with confirmed diagnosis of PsA using CASPAR criteria and with baseline total TJC and SJC counts ≥ 3 at selected study sites

- Change from baseline in Patient's Global Assessment VAS, among subjects with confirmed diagnosis of PsA using CASPAR criteria and with baseline total TJC and SJC counts ≥ 3 at selected study sites
- Change from baseline in Investigator's Global Assessment VAS, among subjects with confirmed diagnosis of PsA using CASPAR criteria and with baseline total TJC and SJC counts ≥ 3 at selected study sites
- Achievement of an ACR 20, among subjects with confirmed diagnosis of PsA using CASPAR criteria and with baseline total TJC and SJC counts ≥ 3 at selected study sites
- Investigator's global assessment among subjects with confirmed diagnosis of PsA using CASPAR criteria and with baseline total TJC and SJC counts ≥ 3 at selected study sites
- Change from baseline in CRP, among subjects with confirmed diagnosis of PsA using CASPAR criteria and with baseline total TJC and SJC counts ≥ 3 at selected study sites
- Change from baseline in TJC and SJC, among subjects with confirmed diagnosis of PsA using CASPAR criteria and with baseline total TJC and SJC counts ≥ 3 at selected study sites

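### The ANCOVA for continuous Part A endpoints uses one residual variance for all arms; if placebo PASI values are more spread out, as is likely, its standard errors will be misstated

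*SAP*

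**What the plan says.** SAP 10.1.2 sends change in PSS to a stratified van Elteren test. For the rest it says "For other continuous variables, the model based mean and standard error will be presented", and then "The treatment groups will be compared using ANCOVA with treatment group, Baseline value, and stratification factors in the model". It gives no variance structure, does not say whether all arms enter one model, and names no confidence interval. SAP 10.1 adds: "The treatment effect will be evaluated based on a two-sided significance level of 0.05".

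The endpoints concerned are in SAP 10.3.1, among them change from baseline in PASI and "Percent change from baseline in PASI". That section calls them exploratory, and they lie outside the hierarchy in SAP 10.4. Protocol 7.3.3 goes less far: apart from PSS, it summarises the further endpoints descriptively.

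Part A has three groups, because SAP Table 1 pools the two placebo sequences. Protocol 7.7 plans 56 patients in each. The same section states that "the PASI 90 response rate at Week 16 is assumed to be at least 65% in the BI 655066 arm", and that earlier phase 3 trials of other agents "indicate a response rate for PASI 90 of approximately 5% in the placebo arm".

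**The concern.** An ordinary ANCOVA estimates one residual variance and applies it to every arm. Percent improvement in PASI cannot exceed 100. If 65% of an active arm lies between 90 and 100, most of that arm sits in a 10-point band at the ceiling, while placebo patients are free to improve, stay the same or worsen. The active spread is then likely to be the smaller one. Absolute change adjusted for baseline behaves similarly: its residual is that of the Week 16 score, and a PASI 90 responder's Week 16 score is at most a tenth of baseline.

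With two active groups and one placebo group in a model, the pooled variance is pulled towards the active value. The placebo mean then looks more precise than it is, the active means look less precise, and each dose-versus-placebo SE is too small. What is at stake is the stated precision of these exploratory results and the nominal level of their 0.05 comparisons.

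**Working it through.** **1. The plan's own figure.** Protocol 7.7 gives 17 per arm for 95% power at 65% versus 5%, two-sided 5%. The two-proportion formula gives [1.960·√(2·0.35·0.65) + 1.645·√(0.65·0.35 + 0.05·0.95)]² / 0.60² = 4.773/0.36 = 13.26. The continuity correction raises this to (13.26/4)·[1 + √(1 + 4/(13.26·0.60))]² = 16.4, so 17. The figure is reproduced. It rests on response rates alone, and no SD enters it.

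**2. What spreads do the rates allow?** One threshold rate per arm does not fix an SD. As a guide I add the phase I figure in Protocol 1.2: 87% PASI 75 by Week 12, in 31 patients after a single dose. The active arm is then 65% uniform on 90–100, 22% uniform on 75–90, and 13% below 75 with an assumed mean and SD. Placebo is 5% uniform on 90–100 and 95% with an assumed mean of 8 and SD of 15, 25 or 35, which gives overall placebo SDs of 24.0, 30.9 and 39.0.

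| Active patients below PASI 75 (assumed mean, SD) | Active SD | Placebo:active SD ratio |
|---|---|---|
| 60, 10 | 12.8 | 1.9 / 2.4 / 3.1 |
| 40, 20 | 19.8 | 1.2 / 1.6 / 2.0 |
| 20, 25 | 26.5 | 0.9 / 1.2 / 1.5 |
| 8, 25 | 30.2 | 0.8 / 1.0 / 1.3 |

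Most cells exceed 1. With the 87% guide, the ratio drops below 1 only when the active patients below PASI 75 barely improve and the placebo spread is also at its smallest.

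**3. Effect on the SEs.** Take three arms of n, active residual SD 1, placebo residual SD k, and ignore the small contribution from estimating covariate effects.

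- Pooled variance: (k² + 2)/3.
- Contrast, model SE / true SE: √[2(k² + 2) / (3(k² + 1))].
- Placebo LS-mean, model SE / true SE: √[(k² + 2)/3]/k. Active LS-mean: √[(k² + 2)/3].
- Coverage of a nominal 95% interval: 2Φ(1.96 × contrast ratio) − 1.

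In a pairwise model the pooled variance is (k² + 1)/2. With equal n the contrast ratio is exactly 1; the by-arm ratios are √[(k² + 1)/2]/k for placebo and √[(k² + 1)/2] for active.

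| k | Three-arm contrast | Coverage | Three-arm placebo / active mean | Pairwise placebo / active mean |
|---|---|---|---|---|
| 1 | 1.00 | 95.0% | 1.00 / 1.00 | 1.00 / 1.00 |
| 1.5 | 0.93 | 93.3% | 0.79 / 1.19 | 0.85 / 1.27 |
| 2 | 0.89 | 92.0% | 0.71 / 1.41 | 0.79 / 1.58 |
| 3 | 0.86 | 90.7% | 0.64 / 1.91 | 0.75 / 2.24 |

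**4. Simulation check.** The ANCOVA was simulated with 56 per arm, a baseline covariate and two binary strata, 5,000 trials per ratio. Three-arm coverage was 93.4%, 92.0% and 90.5% at k = 1.5, 2 and 3. Pairwise coverage was 94.8% to 95.1% for k from 0.5 to 3. In a further run of 6,000 trials per ratio, three-arm HC3 intervals covered 94.7% to 95.8% over the same range of k.

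**The case against.** A reader might infer something stronger: that the response rates imply very different spreads, and that the reported standard errors and confidence intervals are therefore wrong. The documents do not support that, for four reasons.

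- **The rates do not fix the SDs.** If the phase I guide is dropped and the 35% of active non-responders are spread evenly over 0–90, the active SD is 28.5. Placebo shapes with SDs of 27.6 or 21.7 then give ratios of 0.97 or 0.76. The phase I guide is itself a small single-dose result at Week 12, not a planning figure for Week 16. This stands, and is why the ratio is stated as an assumption. One counterexample fails: a normal shift with equal SDs of 25 needs an active mean of 90 + 0.385 × 25 = 99.6, so 49% of patients would exceed 100% improvement (39% at SD 15).
- **No interval is planned.** SAP 10.1.2 names none; the formula in 10.1.1 is for categorical variables and does not pool variances across arms. The coverage figures therefore describe any interval, or equivalent two-sided 0.05 test, built on these SEs.
- **The model may be pairwise.** SAP 10.1.1 and the PSS code in 10.1.5 compare two arms at a time. With 56 against 56 the contrast SE would then be right. This stands for the contrast but not for the by-arm SEs, which 10.1.2 undertakes to present.
- **Little depends on it.** The endpoints are exploratory. Protocol 7.3.3 also asks for SD and IQR, so unequal spread would be visible. In Part B every arm receives risankizumab, so the placebo argument does not carry over. All this stands, and limits the point to a cheap improvement.

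**Conclusion.** The point holds as a conditional one about exploratory Part A endpoints. The SAP specifies a single residual variance by default, and a larger placebo spread is likely but not implied by the plan. On the assumed placebo:active SD ratio:

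- At 1 there is no error.
- At 1.5 to 3, a three-arm model makes the dose-versus-placebo SE 7% to 14% too small. The real level of a nominal 5% test would be about 7% to 9%.
- At 2, by-arm SEs are off by −29% (placebo) and +41% (active) in a three-arm model, and by −21% and +58% in a pairwise one.
- Below 1 the direction reverses.

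The argument is made for PASI change and percent change. For other continuous endpoints the documents give no basis for a size. The primary PASI 90 test and the conclusion on efficacy are unaffected.

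**What to change.** In SAP 10.1.2, for the Part A LS-mean standard errors and placebo contrasts, fit the same ANCOVA with a separate residual variance per treatment group and Kenward-Roger or Satterthwaite degrees of freedom (in SAS, PROC MIXED with a REPEATED statement and GROUP=treatment). HC3 standard errors are an acceptable alternative. State in the same sentence whether the model holds all three arms or is fitted pairwise.

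The cost is one sentence and about one line of code. There are slightly fewer degrees of freedom. In a three-arm fit the dose-versus-placebo SEs will be somewhat larger if the placebo spread is the greater one. If the variances turn out equal, almost nothing is lost.
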